7.7 Wealth quintiles

Socioeconomic questions were collected through a household survey questionnaire. Data from this trial will be compared to each ABCD country's most recent Demographic & Health Survey (DHS) coding for the corresponding wealth/asset variable in the corresponding country. By appending ABCD data and DHS household dataset for each country, DHS wealth index guidelines will be used to perform Principal Component Analysis (PCA) to compute a wealth index score for each observation in the DHS and ABCD datasets all together for a particular country and then take quintiles of that score to assign each participant household a quintile. Since the DHS are nationally representative, the wealth quintile for each ABCD participant is normed to each participant's country standards. Further exploratory analysis by rural vs urban site may also be undertaken.

8 Data missingness and outliers

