10.3 Sample size

For the purposes of sample size determination for the ABCD trial, we have estimated that the 180-day mortality in the control group will be 2.7%. Assuming this baseline mortality, a relative risk in the intervention group of 0.65 (35% reduction in mortality in the intervention group), 90% power, 95% confidence, assumed loss to follow-up 10%, and 1:1 ratio in the numbers of participants in the control and intervention group, the required sample size would be 5,696 per group or 11,392 in total. Since there is an initial plan to conduct one interim analysis for safety (under Fleming bounds, assuming equally spaced analyses and maintaining total $\alpha=0.05$ and $\beta=0.1$, and two-sided symmetric bounds), the sample size will be inflated by a factor of 1.009¹. Hence, the total planned sample size will be 5,750 per group and 11,500 in total.

The estimated overall mortality in the control group is a summary function of earlier data from the GEMS study as well as the assumed proportions of children with various risk factors in the sample and respective sub-group specific mortality rates. The 60-day mortality rate in children under five years of age with moderate to severe diarrhoea or dysentery in the GEMS study averaged 2.0% across all sites. Excluding the two low mortality sites in Bangladesh and West Bengal (India), this mortality rate was 2.8%. The mortality estimates for children with various degrees of stunting or wasting come from GEMS 1a study (which covers children with less severe diarrhoea), supported by meta-analyses of some 10 child cohorts, collected between 1977 and 1997 (Black et al, Lancet Nutrition Series 2008; Olofin et al PLoS One, 2013).

As the study is implemented in 7 countries, on average each country will need to enroll 1645 children (about 822 per study group). Over an enrolment period of 30 months, this would mean approximately 13 children/country will need to be enrolled per week. Individual sites will be allowed to enroll up to 2000 study subjects until the total sample size is achieved.

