4.5 Effect modification of treatment effects

We will examine whether treatment effects on the outcomes (primary and secondary) differ by *a priori* determined effect modifiers. We will examine modification of treatment effects by trial site by including effect modifying covariates in the regression models.

Effect modifiers of interest include:

1. The participant's age (examined as a continuous variable, but reported as <6 months of age, 6-11 months, 12 months or older)
2. The participant's sex
3. Reason for enrolment: dehydration, moderate wasting or severe stunting considered as non-mutually exclusive categories
4. Participant's wealth quintile with respect to country-specific national wealth distribution (see derivation in Section 7.7)

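### Wealth quintiles are cut on survey and trial households pooled, so they are not normed to the national distribution as SAP 7.7 states and 4.5 requires

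*SAP*

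**What the plan says.** SAP 4.5 lists four effect modifiers fixed in advance. One is the participant's "wealth quintile with respect to country-specific national wealth distribution", and it refers to 7.7 for the derivation.

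SAP 7.7 appends the trial data to the most recent DHS household file for the same country. Citing DHS wealth index guidelines, it plans a principal component analysis (PCA) whose purpose is to "compute a wealth index score for each observation in the DHS and ABCD datasets all together for a particular country". The pooled score is what gets cut into fifths, and every trial household is placed in one of them. The justification follows: "Since the DHS are nationally representative, the wealth quintile for each ABCD participant is normed" to that participant's country.

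The section does not say that loadings or cut-points come from the survey households alone, and it mentions no survey weights. The content of the cited guidelines is not reproduced in either document.

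Wealth quintile is in the covariate vectors of Model 2 (mortality, SAP 9.1), Model 5 (change in length-for-age, 9.2) and Model 7 (hospitalization, 9.3). It carries over by analogy to the other anthropometric outcomes (9.4.1) and is among the covariates for the exploratory resistance analyses (9.5.3, 9.6.4). The primary analyses of mortality and length-for-age leave it out.

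**The concern.** The reason given for national norming concerns the survey, but the cut-points are taken from a different file: the survey plus a sample recruited at health facilities. A fifth of the pooled file is not a fifth of the nation unless the trial families have the national wealth distribution. Where they do not, each cut-point moves, and by more where the trial is a larger part of the pooled file. Pooling can also alter the PCA loadings.

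What is at stake is the meaning of a pre-specified subgroup variable. A child labelled as in the lowest national quintile may not be. Because the trial share and the wealth difference can vary by country, the same label can stand for a different national rank in different countries.

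**Working it through.** **The plan's own figure.** The plan states no number for the quintiles. The only stated input to the trial's share of the pooled file is average enrolment per country, given as 1,645 in Protocol 10.3. Check: 11,500 / 7 = 1,642.9, which agrees to rounding.

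**Inputs.**
- Trial households per country: 1,645, counting one household per child. Protocol 10.3 also allows up to 2,000 per site. Both are planned numbers; recruitment stopped early (SAP 2) and the final numbers are not given.
- Survey households per country: not given. Assumed 5,000 to 600,000.
- Trial wealth relative to the nation: not given. Assumed mean difference d of 0, or 0.25 to 1 national SD in either direction, with trial spread s equal to the national SD or 0.6 of it.

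**Model.** Let national wealth be standard normal, and let w = trial households / (trial + survey households). The pooled distribution is

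F(x) = (1 − w)·Φ(x) + w·Φ((x − d)/s).

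Solve F(x) = 0.2, 0.4, 0.6 and 0.8 for the pooled cut-points and read each back as a national percentile Φ(x). The share of trial households that change quintile is the sum over the four cuts of |Φ((pooled cut − d)/s) − Φ((national cut − d)/s)|.

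**One case by hand.** With 5,000 survey households, w = 1,645 / 6,645 = 0.248. Take d = −0.5 and s = 1. The lowest pooled cut falls at national percentile 16.2, below which 31.4% of trial households lie. Check: 0.752 × 0.162 + 0.248 × 0.314 = 0.122 + 0.078 = 0.20. The four cuts sit at national percentiles 16.2, 35.2, 55.5 and 77.0. The share of trial households in the lowest quintile is 31.4%, against 36.6% with survey-only cuts. Over all four cuts, 15.7% change quintile.

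**Trial households changing quintile, 1,645 per country:**

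| Survey households | Trial share w | 0.25 SD, s = 1 | 0.5 SD, s = 1 | 1 SD, s = 1 | 1 SD, s = 0.6 |
|---|---|---|---|---|---|
| 5,000 | 24.8% | 8.1% | 15.7% | 26.9% | 36.1% |
| 10,000 | 14.1% | 4.6% | 8.9% | 14.8% | 20.4% |
| 20,000 | 7.6% | 2.5% | 4.8% | 7.8% | 10.8% |
| 100,000 | 1.6% | 0.5% | 1.0% | 1.6% | 2.3% |
| 600,000 | 0.3% | 0.1% | 0.2% | 0.3% | 0.4% |

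With d = 0 and s = 1 the figure is 0% at every survey size. The largest value in any run was 41.8% (2,000 trial and 5,000 survey households, 1 SD, s = 0.6).

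**Direction.** If trial families are poorer, the cuts fall and some children are placed in too high a quintile. If they are richer, the cuts rise and some are placed too low. The percentages are the same for a shift of equal size either way.

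**After the fix.** Survey-only cut-points sit at national percentiles 20, 40, 60 and 80 by construction, so no household is reclassified through the cuts.

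The change in PCA loadings caused by pooling was not quantified.

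**The case against.** The case against making much of this is strong on consequences.

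- **Size.** The documents show neither how large the surveys are nor how trial wealth compares with national wealth. A large survey or similar wealth makes the effect negligible. This stands: material misclassification is possible but not shown.
- **Direction.** A reader might infer that trial families are poorer everywhere, so that every cut-point falls. Protocol 13.1 and 13.6 point that way for Bangladesh and Pakistan. But recruitment in Malawi (13.4), Tanzania (13.7) and part of Mali (13.5) is urban or peri-urban, no wealth rank is given, and the comparison is with the whole nation. The direction is not established.
- **Reach.** A reader might infer that every primary and secondary result depends on this variable. It does not. The primary models omit it. Baseline *E. coli* resistance (SAP 5) and cause-specific mortality (9.7) are descriptive. The resistance covariates are exploratory. SAP 10.1 doubts whether effect modification can be examined for mortality at all, since deaths are few.
- **Bias.** The index is built without reference to arm in a blinded trial, so any error is unrelated to allocation. In every run the cut-points moved by less than one quintile, so the households that change lie close to a cut, and the ordering on the pooled score does not depend on where the cuts fall.
- **Unseen guidelines.** The cited guidelines might prescribe weights or survey-only cut-points, and 7.7 does not expressly exclude them. Its plain wording nevertheless takes quintiles of the pooled score, and no other section corrects that.

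These points limit the consequence. They do not rescue the statement of national norming.

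**Conclusion.** Wrong as written, minor. The procedure in SAP 7.7 does not yield the quintile that 4.5 defines, and the reason offered for national norming does not follow once trial households are in the file that is cut. The reclassification runs from 0% to about 42% of trial households over all the assumed ranges. With equal spread and 1,645 trial households it is about 8-27%, 2.5-8%, or under 2%, for surveys of 5,000, 20,000, or at least 100,000 households. These figures rest on assumed survey sizes, assumed wealth differences, a normal model and planned enrolment.

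The consequence is confined to the label of one effect modifier, its comparability across countries as a national rank, and the adjusted and exploratory models that include it. The documents do not support the stronger inference that the modifier is materially misclassified, or that the treatment comparison is biased.

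**What to change.** In SAP 7.7, estimate the loadings and the four cut-points for each country in the DHS households alone, with the survey's weights, and then score and classify trial households with those values. Only assets recorded in both sources can be used, which the matching of variables in 7.7 already implies. If the pooled derivation is kept, drop the statement that the quintiles are nationally normed, align the definition in 4.5, and report the trial share of the pooled file by country.

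The cost is a change to the analysis program and a sentence or two in 7.7. No new data are needed.

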8.1 Missingness

Every effort will be made to ensure as complete data recording as possible. Inbuilt database checks on missing fields are pre-programmed and regular quality assurance checks will be conducted at sites. Missingness prevalence and pattern will be reviewed by trial statisticians. In describing the trial cohorts, where missingness is $>10\%$ the missing will be reported as a separate category. Missingness of primary outcomes is addressed in Section 4.1. Participants with no recorded death events will be presumed alive for analysis of Primary Outcome 1. Participants with missing anthropometry or age data at day 1 or at day 90, for which change in length-for-age z-score is not possible, will be excluded from analysis for Primary Outcome 2 (change in length-for-age z-score) and Secondary Outcome 1 (acute wasting). Children who develop bi-pedal edema and cannot have a weight associated z-score will be included in Primary Outcome 1 but excluded from Secondary Outcome 1. Complete case analyses will be performed and missing anthropometry data will not be imputed. The investigators considered imputation methods to be unlikely to result in valid predictions of individual level anthropometric measures.

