2.3 Eligibility criteria

2.3.1 Inclusion criteria (all of):

- Children aged 2 – 23 months, presenting to a designated health care facility at a participating study site **WITH**
- Diarrhoea per caregiver perception **AND** at least 3 loose or watery stools in the previous 24 hours,
- Diarrhoea for less than 14 days prior to screening **AND** with at least one of the following criteria at presentation:
 - A. Signs of some or severe dehydration as per WHO Pocket Book 2013

- B. Moderately wasted as defined by a mid-upper arm circumference (MUAC) less than 125 mm (but greater than or equal to 115 mm) or a weight-for-length z-score (WLZ) greater than -3SD and less than or equal to -2SD after rehydration during stabilization period or
- C. Severely stunted (length-for-age z-score (LAZ) <-3 SD) **AND**
- Parent or guardian (caregiver) willing to allow household visits on DAY 2 and DAY 3 and willing to return to facility on DAY 90 **AND**
- Parent or guardian (caregiver) provides a consent for trial participation on behalf of the child, based on local standards

Exclusion criteria (any one of):

- Dysentery (gross blood in stool reported by caregiver or observed by healthcare worker [HCW]),
- Suspected *Vibrio cholerae* infection (determined according to WHO guidelines or clinical suspicion),
- Previously or currently enrolled in the ABCD study,
- Concurrently enrolled in another interventional clinical trial,
- Sibling or other child in the household enrolled in the ABCD study and currently taking study medication,
- Signs of associated infections (pneumonia, severe febrile illness, meningitis, mastoiditis or acute ear infection) requiring antibiotic treatment,
- Documented antibiotic use in the 14 days prior to screening (not including standard use of prophylactic antibiotics, i.e. co-trimoxazole use in HIV-exposed children),
- Documented use of metronidazole within the last 14-days,
- Known allergy or contraindication to azithromycin antibiotics,
- Severe acute malnutrition (SAM) defined as WLZ less than -3 SD, or MUAC less than 115 mm, or edema of both feet, OR
- Living too far from the enrolment health center to ensure adequate Directly Observed Therapy (DOT) on DAY 2 and DAY3

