10.2 Secondary Objectives

1. *To compare changes in markers of acute malnutrition (Δ MUAC and Δ WLZ and Δ weight) in the 90 days following an episode of high risk diarrhoea without dysentery among children 2 to 23 months of age living in low resource settings who are randomized to receive a 3-day course of azithromycin or placebo.*

Linear regression (and associated z-test) will be used to compare mean Δ MUAC and Δ WLZ and weight across the treatment groups among surviving children.

2. *To evaluate (as determined by Verbal and Social Autopsy – VASA) cause-specific mortality rates across randomization arms in the 180 days following an episode of high risk diarrhoea without dysentery among children 2 to 23 months of age living in low resource settings who are randomized to receive a 3-day course of azithromycin or placebo.*

We will conduct Cox regression and K-M survival analyses (as described for aim 1) for time to cause-specific mortality (diarrhoea, pneumonia, malnutrition, other) as separate endpoints to understand intervention effects on specific causes of death.

3. *To compare the proportion of children hospitalized in the 90 days following enrolment for an episode of high risk diarrhoea without dysentery among children 2 to 23 months of age living in low resource settings who are randomized to receive a 3-day course of azithromycin or placebo.*

4. *To compare the proportion of children hospitalized or dying in the 90 days following enrolment for an episode of high risk diarrhoea without dysentery among children 2 to 23 months of age living in low resource settings who are randomized to receive a 3-day course of azithromycin or placebo.*

5. *To compare the proportion of children hospitalized or dying in the initial 10 days following enrolment for an episode of high risk diarrhoea without dysentery among children 2 to 23 months of age living in low resource settings who are randomized to receive a 3-day course of azithromycin or placebo.*

6. *To compare the presence of strains of *E. coli* resistant to selected antibiotics at enrolment between children in the different treatment arms entering the trial over time. Since children entering later into the trial are coming from the same communities, they can serve as a comparator group indicative of the community level of resistance.*

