Null hypothesis: Among children 2 to 23 months of age with moderate to severe diarrhea, the proportion of children hospitalized or dying by D90 after enrolment, is independent of treatment allocation to placebo or to a 3-day course of oral azithromycin.

Alternative hypothesis: Among children 2 to 23 months of age with moderate to severe diarrhea, the proportion of children hospitalized or dying by D90 after enrolment, is not equal in the placebo arm and the arm receiving 3-day course of oral azithromycin.

Secondary objective 3 – Hospitalization or death by day 10

Null hypothesis: Among children 2 to 23 months of age with moderate to severe diarrhea, the proportion of children hospitalized or dying by day 10 after enrolment, is independent of treatment allocation to placebo or to a 3-day course of oral azithromycin.

Alternative hypothesis: Among children 2 to 23 months of age with moderate to severe diarrhea, the proportion of children hospitalized or dying by day 10 after enrolment, is not equal in the placebo arm and the arm receiving 3-day course of oral azithromycin.

Secondary Objective 4, 5 & 6 - Acute wasting:

Null hypothesis: Among children 2-23 months of age with moderate to severe diarrhea, the mean change from baseline in weight-for-length z-score (ΔWLZ), weight-for-age z-score (ΔWAZ) and mid-upper arm circumference ($\Delta MUAC$) over the 90 day follow-up period is independent of treatment allocation to placebo or to a 3-day course of oral azithromycin.

Alternative hypothesis: Among children 2-23 months of age with moderate to severe diarrhea, the mean change from baseline in weight-for-length z-score (ΔWLZ), weight-for-age z-score (ΔWAZ) and mid-upper arm circumference ($\Delta MUAC$) over the 90 day follow-up period is not independent of treatment allocation to placebo or to a 3-day course of oral azithromycin.

Secondary objective 7: descriptive report of prevalence of azithromycin resistant *E.coli* from stools provided at baseline by a sub sample of children enrolled into the trial.

Secondary Objective 8- Antibiotic resistance:

Null hypothesis: Among the subset of children 2-23 months of age with moderate to severe diarrhea selected to be in the AMR sub-study, the prevalence of resistance to azithromycin in *E. coli* and *S. pneumoniae* is greater than or equal to 10% points higher in the group randomized to a 3-day course of oral azithromycin than those randomized to placebo.

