8.2 Outliers

The WHO Growth Standards 2006 (Page 14 in https://www.who.int/childgrowth/software/anthro_pc_manual_v322.pdf) consider the following metrics as biologically implausible and recommend excluding these from analysis of nutritional surveys:

WAZ <-6 or >5 , or LAZ <-6 or >6 , or WLZ <-5 or >5

Data points outside these bounds will be considered missing and excluded from analysis for Primary Objective 2 and Secondary Objective 1, both for the Per Protocol and the Intention to Treat cohorts. It should be noted that trial inclusion/exclusion criteria excluded from enrolment children with WLZ ≤ -3 at baseline.

Participants whose length on day 90 is less than their length on day 1 will have the respective z-scores calculated and will remain included in analysis for Primary outcome 2. This is because there is likely to be bidirectional bias in repeated measurements. Negative deviances in length are likely to occur only rarely, while similar sized positive deviance in length are difficult to distinguish from correctly recorded gains in length over time. Excluding the negative results only would bias the total cohort towards a larger difference from baseline. Keeping them in the cohort is the more conservative option.

9 Statistical analyses

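### SAP 8.1 applies one child-level exclusion to all acute-wasting outcomes, so usable MUAC and weight-for-age data are dropped under a label that no longer names those outcomes

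*SAP*

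**What the plan says.** SAP 8.1 sets two exclusion rules for anthropometry.

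- **Unusable length or age.** Participants with missing data at day 1 or day 90 "for which change in length-for-age z-score is not possible, will be excluded from analysis for Primary Outcome 2". The same sentence extends this to the wasting outcomes: "change in length-for-age z-score) and Secondary Outcome 1 (acute wasting".
- **Oedema.** Children in whom bipedal oedema appears, and for whom no weight-based z-score can be given, "will be included in Primary Outcome 1 but excluded from Secondary Outcome 1". Primary Outcome 1 is mortality. The sentence does not mention LAZ (Primary Outcome 2) or MUAC.

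SAP section 5 sets the scope of acute wasting. Under "Secondary Objective 4, 5 & 6 - Acute wasting" it lists change in WLZ, WAZ and MUAC. Protocol 10.2 has a similar first secondary objective: "To compare changes in markers of acute malnutrition (Δ MUAC and Δ WLZ and Δ weight) in the 90 days".

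SAP 8.2 gives plausibility bounds for WAZ, LAZ and WLZ and adds: "Data points outside these bounds will be considered missing and excluded from analysis for Primary Objective 2 and Secondary Objective 1". SAP 8.1 analyses complete cases and does not impute anthropometry.

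**The concern.** An exclusion rule for an outcome should depend on what that outcome is computed from. Here, failure of one measure (length) removes a child from others that do not use it, and a reason about weight-based scores is attached to a block that includes arm circumference.

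Two things are at stake. Valid secondary-outcome data are discarded. Also, if MUAC is dropped under oedema, the MUAC comparison is conditioned on a sign that arises after randomization and that the protocol counts as deterioration in the same domain. Protocol 2.3 reads: "Severe acute malnutrition (SAM) defined as WLZ less than -3 SD, or MUAC less than 115 mm, or edema of both feet". SAP 8.2 avoids this kind of selection elsewhere: it keeps children whose length appears to shrink, because removing only those would bias the result.

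The outdated number adds a reproducibility problem. Two analysts could build different datasets from the same text.

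**Working it through.** No figure in the documents depends on these rules, so the check is mainly of text, followed by an illustration of size.

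**1. What each measure needs, against what 8.1 does.** Inputs are from SAP 7.2, the two sections numbered 7.3, and 9.4.1.

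| Change in | Inputs | Only length unusable | Only age missing | Bipedal oedema |
|---|---|---|---|---|
| LAZ | length, age, sex | properly lost | properly lost | usable; 8.1 silent |
| WAZ | weight, age, sex | usable but dropped | properly lost | properly lost |
| WLZ | weight, length (7.3 also lists age and sex) | properly lost | depends on whether the growth macro needs age | properly lost |
| MUAC | two MUAC readings | usable but dropped | usable but dropped | usable but dropped, reading 8.1 with section 5 |

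No other section restores the dropped cells.

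**2. Out-of-range LAZ.** Under 8.2 such a value counts as missing. Change in LAZ then cannot be computed, so the first rule in 8.1 removes the child's WAZ and MUAC as well. If the cause is a wrong age, WAZ is suspect too; if it is a wrong length, it is not.

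**3. Numbering.** In SAP 3.2, item 1 is at least one hospitalization by day 90, and wasting is items 4 to 6. SAP 4.2 and the first rule in 8.1 use the old number but add the words for acute wasting. The oedema sentence and 8.2 use it with no label, so read literally they point to hospitalization.

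**4. Visibility.** SAP Table 3 has a single row for day-90 anthropometry performed. Losses by measure would not show.

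**5. Size: unusable length.** All rates below are assumptions, because the documents give none.

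- Children followed: 11,500 × (1 − 0.10) = 10,350, using the planned total and the 10% loss in protocol 10.3.
- Share f with only length unusable: 0.5% to 5%.
- Pairs lost per measure: 10,350 × 0.005 ≈ 52, to 10,350 × 0.05 ≈ 518.
- SE inflation is 1/√(1 − f) − 1: 1/√0.995 − 1 = 0.25%, to 1/√0.95 − 1 = 2.6%.

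**6. Size: oedema and MUAC.** Let q0 and q1 be the shares with oedema on placebo and azithromycin, and L the deficit in MUAC change among children with oedema. If the arms differ only through oedema, the difference removed is (q0 − q1) × L.

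- Low: (0.001 − 0.0005) × 0.5 cm = 0.00025, about 0.0003 cm.
- High: (0.02 − 0.01) × 2 cm = 0.02 cm.

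These values assume that azithromycin halves oedema, which favours finding an effect.

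**The case against.** **MUAC is never named in 8.1.** The oedema sentence is limited to children without a weight-based z-score; MUAC is not one, and 9.4.1 and Table 3 treat it separately. This stands as a point of ambiguity: dropping MUAC under oedema is inferred from section 5. It does not rescue the first rule, which names acute wasting outright.

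**Length, weight and MUAC are taken at the same visits.** A missed visit loses all three, whatever the rule says. This stands and limits the loss to children measured with one bad or missing component.

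**The outdated number is editorial.** Largely so. It matches protocol Secondary Objective 1, and few analysts would apply an oedema rule to hospitalization. It still needs correcting where no label accompanies it.

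Three stronger readings are tempting, and the documents do not support them:

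- A reader might infer that children whose malnutrition became severe are removed in general. Only bipedal oedema triggers the rule. Severe wasting without oedema stays in: 8.2 keeps WLZ down to −5 and sets no MUAC bound.
- A reader might infer that such deterioration could then not be detected at all. Children with oedema remain in mortality, and on the evident intent of 8.1 in the hospitalization outcomes too; severe wasting without oedema still moves the anthropometric means.
- A reader might infer that a weight error removes a valid LAZ under 8.2. That rule speaks of data points, so it most naturally blanks only the offending score. Likewise, nothing in 8.1 takes a child with oedema out of the LAZ analysis; the text merely does not say so.

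**Conclusion.** The point holds for the first rule as written: valid MUAC data, and valid WAZ data when only length is unusable or LAZ is out of range because of length, are discarded without reason. For oedema it holds for MUAC when 8.1 is read with section 5; excluding WLZ and WAZ is correct. The numbering in 4.2, 8.1 and 8.2 is out of date.

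Materiality is not shown. Under the assumed rates, the SE rises by 0.25% to 2.6% and the mean MUAC difference moves by 0.0003 to 0.02 cm. The counts of 52 to 518 use the planned enrolment; SAP section 2 records that recruitment was halted early, so the same rates would give fewer children in the actual cohort. No conclusion is shown to change. The case for amending rests on validity and reproducibility, at almost no cost.

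**What to change.** Before the intervention code is broken, replace the block rule in SAP 8.1 with an analysis set for each measure:

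- **LAZ change:** valid length and age at both visits.
- **WAZ change:** valid weight and age at both visits, no oedema.
- **WLZ change:** valid weight and length at both visits, no oedema; say whether age is also required, since 7.3 lists it.
- **MUAC change:** both MUAC readings.

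State that children with oedema stay in the LAZ and MUAC analyses, and that each 8.2 bound applies only to the z-score that breaches it. In 4.2, 8.1 and 8.2, replace the old Secondary Outcome or Objective 1 with Secondary Objectives 4 to 6. Report by arm the number of children with unusable length and, where recorded, with oedema.

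The cost is a few lines of SAP text, slightly different denominators across measures and a short table. A tabulation of day-90 severe acute malnutrition by arm is optional and should be descriptive only: it is not a stated objective, and protocol 6.2 and 6.4 list weight, length and MUAC at day 90 without a systematic oedema check.
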